## 7.5. PK/PD Analyses

The dose- and exposure-response relationship between baseline-adjusted AUEC for neopterin and  $\Delta\text{Neopterin}_{\text{dec, max}}$  and IFN  $\beta$ -1a and pegIFN  $\beta$ -1a will be explored graphically (separate assessments for both response measures). Based on these observations, model-based analyses using statistical software will be conducted separately for each drug with respect to each of the above-mentioned PD measures.

The model-based analysis will explore both dose and exposure (i.e.,  $AUC_{0-\text{inf}}$ , referred to as AUC below) as the dependent variable. Data for all dose levels for a drug, as well as placebo, will be combined for the analysis. Model selection will be based on the initial graphical assessment and will be selected from one of the following structures – linear,  $E_{\text{max}}$ , and sigmoidal. Multiple models may be evaluated based on the initial graphical analysis, in which case model selection will be based on a combination of goodness of fit plots, parameter uncertainty (i.e., parameter confidence intervals including zero), and Akaike’s information criterion (AIC). General representations for each of the model structures and parameterizations is shown below:

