## Change Log

Version	Section	Changes
2	5	Added that ‘Subjects who did not complete their treatment (referred to as early termination subjects) will not be included in PK and PD parameter summary calculations.’
2	7.3.1, 7.3.2	The descriptive summary for PD parameters is changed from geometric mean to mean. Changes in PD parameter from baseline for placebo and low doses may have negative values and would not allow for calculation of geometric mean. Text describing the primary, secondary, and exploratory PD parameter was updated for clarity.
2	General	Typographical changes included throughout

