### 4.2. Secondary Endpoints

- Area under the curve (AUC) of IFN  $\beta$ -1a and pegIFN  $\beta$ -1a from time zero to infinity (AUC0-inf)
- Maximum concentration (Cmax) of IFN  $\beta$ -1a and pegIFN  $\beta$ -1a

- $AUEC_{0-t}$  of MxA protein.
- Maximum increase from baseline in MxA protein ( $\Delta MxA_{dec, max}$ )
- Model parameter estimates for IFN  $\beta$ -1a and pegIFN  $\beta$ -1a exposure-response models (exposure parameter versus  $AUEC_{0-t}$  or  $\Delta Neopterin-C_{min}$ )

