## 5. Analysis Populations

- For all analyses, subjects will be analyzed according to the dose and treatment received, not the dose and treatment to which subjects were randomized.
- Subjects who discontinued from the study before their assigned end of study day (referred to as early termination subjects) will be excluded from pharmacokinetic and pharmacodynamic parameter summary calculations.
- The PD population will include all subjects who received study drug and have at least 1 estimable PD parameter after dosing. For baseline-adjusted analyses, subjects must also have at least one valid baseline sample between screening to dose administration on day 1. Subjects without a valid baseline sample will be excluded from PD assessments where the derived metric is baseline adjusted.
- The PK population will include all subjects who received study drug and have at least 1 estimable PK parameter after dosing. Subjects with all samples below the lower limit of quantification will not be included in PK population summaries.
- The PK/PD population (exposure-response population) will be used for the model-based exposure-response analysis. This population includes all subjects from the PK and PD populations, including those who received placebo treatment, as well as subjects with PK samples below the lower limit of quantification.

- The safety population will include all subjects who received at least 1 dose of any of the study drugs,

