## **6. Data Screening and Acceptance**

### **6.1. Handling of Missing and Incomplete Data**

The following imputation of missing values will be done:

- Pharmacokinetic measurements below the quantification limits will be considered equal to zero for all analyses.
- Non-pharmacokinetic measurements (e.g., neopterin, MxA) below the quantification limits will be considered equal to the lower limit of quantification for all analyses unless explicitly noted otherwise.
- Missing pharmacokinetic or pharmacodynamic data (e.g., skipped outpatient visit) will not be imputed.
- For baseline adjusted measures, samples from Day 1, time 0 will be used for calculating this derived metric. In cases where the Day 1, time 0 sample is missing or invalid, the sample collected at check-in (Day -1) will be used, followed by the screening sample. If none of these samples are available or valid, then no baseline value will be calculated for the subject.

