### **7.3. Pharmacodynamic Analysis**

#### **7.3.1 Neopterin**

Individual neopterin versus time plots will be presented for each participant. For neopterin, AUEC and maximum increase from baseline will be calculated for each participant using all on treatment timepoints. Calculations will be performed using non-compartmental analysis packages available in statistical software. The primary analysis with neopterin will use baseline-adjusted AUEC and maximum increase from baseline, while other derived measures (AUEC, pAUEC) may be calculated to evaluate how derived PD metrics impact trial design. PD parameters of IFN  $\beta$ -1a and pegIFN  $\beta$ -1a, and placebo groups will be listed and summarized using descriptive statistics (n, mean, SD, coefficient of variation, minimum, median, interquartile range, and maximum) for each treatment arm.

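### SAP 7.5 can select a linear model, and nothing in the SAP then requires the Emax and EC50 that protocol 4.2 makes a secondary endpoint

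*SAP*

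**What the plan says.** - **Protocol 4.2**, third secondary endpoint: Emax and EC50, from a model fitted to the three dose levels combined with placebo. **Protocol 5.9.6.1** evaluates each subject's AUEC under an assumed saturating Emax relationship.
- **SAP 4.2** states the corresponding endpoint generically: "Model parameter estimates for IFN" β-1a and pegIFN β-1a exposure-response models. It does not name Emax or EC50 there.
- **SAP 7.5** takes the form from linear, Emax or sigmoidal after a graphical look. Several models may be evaluated, "in which case model selection will be based on a combination of goodness of fit plots", with "parameter uncertainty (i.e., parameter confidence intervals including zero" and AIC as the other two criteria. It gives no weights or order and exempts no parameter. E0 is a free parameter in all three forms.
- **Data in the fit (SAP 7.5):** "Data for all dose levels for a drug, as well as placebo, will be combined for the analysis".
- **Response (SAP 7.3.1):** "The primary analysis with neopterin will use baseline-adjusted AUEC and maximum increase from baseline". The SAP Change Log, explaining the current summary statistics, adds: "Changes in PD parameter from baseline for placebo and low doses may have negative values".

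**The concern.** The protocol fixes the curve and names two of its parameters as an endpoint. The SAP makes the curve a choice and does not say what happens to those parameters if the choice is linear. The trial is meant to inform later similarity studies, including the choice of sensitive doses, and for that purpose Emax and ED50/EC50 are the informative quantities.

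The selection rule also has an avoidable weakness. An interval that includes zero is a sensible warning for a slope or an Emax. It is the wrong test for E0 when the response is a change from baseline and placebo is in the fit. E0 is then the placebo mean change, which a correct model should estimate as close to zero.

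**Working it through.** **1. The endpoint gap, by comparison of texts**

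| | Protocol | SAP |
|---|---|---|
| Endpoint | Emax and EC50 (4.2) | Model parameter estimates (4.2) |
| Curve | Saturating, assumed (5.9.6.1) | Linear, Emax or sigmoidal, selected (7.5) |
| If linear is selected | Does not arise | E0 and slope only |
| Duty to report an Emax fit regardless | Implied by the endpoint | None found |

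Linear can be reached in two ways: from the graphs alone, in which case an Emax model need never be fitted, or through the three criteria. The gap exists in both cases.

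**2. Why the E0 check is not neutral between the models**

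Doses as fractions of the high dose are 0, 0.25, 0.5 and 1 for both drugs (7.5/15/30 µg; 31.25/62.5/125 µg). Let k be ED50 on that scale, true E0 = 0, and the high-dose effect = 1. The true curve is f(d) = (1 + k)d/(d + k). For a least-squares line through the four true means, mean d = 0.4375 and Sxx = 1.3125 − 4 × 0.4375² = 0.5469.

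For k = 0.25, mean f = 0.6146 and Sxy = 1.5729 − 4 × 0.4375 × 0.6146 = 0.4974. The slope is 0.4974/0.5469 = 0.9095 and the intercept is 0.6146 − 0.9095 × 0.4375 = 0.217.

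| ED50 (assumed) | True effect at 0, low, mid, high | Slope | Intercept |
|---|---|---|---|
| low dose | 0, 0.625, 0.833, 1 | 0.910 | 0.217 |
| mid dose | 0, 0.500, 0.750, 1 | 0.943 | 0.150 |
| high dose | 0, 0.400, 0.667, 1 | 0.968 | 0.093 |

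The wrong model has an intercept pushed away from zero and so tends to pass the check. In the first row the line gives 0.217 + 0.910 × 0.25 = 0.444 at the low dose against a true 0.625 (−29%), and 1.126 at the high dose (+13%).

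**3. How often, under assumptions**

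The documents give no SD, ED50 or interval level for this check, so these are ranges. Simulation: dose model, true Emax curve with E0 = 0, 12 subjects per level (SAP 3.2), normal constant error, 95% Wald intervals, 2,000 to 3,000 trials per cell. Fit plots and the sigmoidal form were not modelled. Triples are ED50 = low/mid/high dose; entries are % of trials.

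| SD, % of high-dose effect | E0 interval includes zero: Emax fit | Same: linear fit | E0 flags Emax only, and AIC prefers Emax | E0 flags Emax only, and AICs within 2 units |
|---|---|---|---|---|
| 20 | 95–96 | 2/16/53 | 94/81/41 | 0/1/9 |
| 30 | 95–96 | 19/48/75 | 78/47/16 | 1/9/11 |
| 50 | 95–96 | 57/76/87 | 37/15/5 | 13/11/8 |

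With 90% intervals at 30% SD, the first two columns become 90–91 and 10/34/63.

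**4. Sensitivity to placebo behaviour (30% SD, 95% intervals)**

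- Placebo SD doubled: the E0 interval in the Emax fit includes zero in about 80% of trials. The fourth column falls from 76/46/15 to 47/21/6 (the starting values are a separate run of the same cell, within simulation error).
- Placebo mean drifting by −10% of the high-dose effect: Emax fit 79–81%, linear fit 70/92/96%. At −20%: 36–37% against 97/93/69%, a reversal.
- Drift of +10%: 79–81% against 1/7/22%.

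**5. ED50 under the same criterion**

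ED50 is positive, so a natural-scale Wald interval that reaches zero shows imprecision and is not evidence of linearity. At 30% SD it reaches zero in 83/87/95% of correct Emax fits with constant error, but in 17/12/43% with proportional error. Over all the assumptions tried it ran from 0% to 100%, so no single figure is claimed.

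**The case against.** **On the endpoint gap.** Choosing a form suits an unpowered pilot whose secondary objective is to explore PK/PD relationships with appropriate models. The SAP abbreviation list defines Emax and EC50 as model parameters, and a forced Emax fit may give uninformative intervals. All of this is fair. A reader might infer that the SAP has dropped Emax and EC50, or that linear will be chosen. Neither is supported: Emax is a candidate form, and its parameters are reported if it is selected. What remains is narrower, namely that delivery depends on the selection.

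**On the E0 check.** This is the stronger objection, and most of it stands.

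- The SAP states no rule that a flag rejects a model. The check is one of three criteria and applies only if several models are evaluated. A raised intercept is lack of fit, which plots and AIC can detect.
- The conflict is greatest where AIC decides clearly. It coincides with AICs within 2 units in only 0% to 13% of trials. AIC's protection is weaker with mild curvature and noisy data: with ED50 at the high dose, AIC preferred Emax in 10.8 of the 20.3% of trials where only Emax was flagged at 35% SD, and in 5.3 of 11.0% at 50% SD.
- The Change Log says low-dose changes may also be negative, which points to the noisier cells. At 20% SD with ED50 at the low dose, the chance of any negative value among 12 low-dose subjects is about 1%; at 50% SD it is 74% to 94%. At 50% SD the conflict with AIC is only 37/15/5%.
- Placebo is followed to Day 14 and Avonex to Day 7 (SAP 3.1), and AUEC runs to the last on-study time point (SAP 4.1). In the Avonex fits the longer placebo window may raise placebo variance and accumulate drift. The doubled SD in step 4 is an assumption prompted by this.

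A reader might infer from the 94% cell that the SAP would usually reject a correct Emax model. The documents do not support that, and the simulation does not estimate it.

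**On the exposure models.** No below-quantification figures are given because the SAP does not settle the input. SAP 5 keeps in the exposure-response population "including those who received placebo treatment, as well as subjects with PK samples below the lower limit of quantification", and SAP 6.1 says "Pharmacokinetic measurements below the quantification limits will be considered equal to zero for all analyses", which suggests AUC = 0. SAP 7.4 includes AUC0-inf only with at least 3 terminal concentrations and adjusted R² above 0.80, which suggests no usable value. These need reconciling first.

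**Conclusion.** The endpoint gap holds as a matter of text and rests on no assumption: the SAP can be carried out completely without delivering Emax and EC50. It is narrow, because it bites only if linear is selected, but it concerns a named secondary endpoint.

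The E0 point holds as a secondary, smaller weakness. With E0 = 0 and equal variances, a correct Emax fit has an E0 interval including zero at about the nominal rate, while the linear intercept is raised by 9% to 22% of the high-dose effect. E0 near zero is itself inferred from baseline adjustment; the documents give no placebo value. The size depends on assumed SD, ED50, placebo drift and placebo variance, and the direction reverses with enough downward drift. The point does not apply to maximum increase from baseline, where the expected placebo value is positive by construction.

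**What to change.** 1. In SAP 4.2 and 7.5, state that Emax and ED50/EC50 from the Emax fit, with intervals, are reported for each drug whichever model is selected, and are marked as poorly identified where the interval is unbounded.
2. In SAP 7.5, do not apply the zero-in-interval check to E0 when the response is baseline-adjusted AUEC. Do not treat an ED50/EC50 Wald interval that reaches zero as sufficient on its own to reject the Emax form when AIC supports it.

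This changes SAP wording only and needs no new data. The cost is some weak estimates in the report. At 30% SD with constant error, a profile interval for ED50 is bounded on both sides in 83/76/43% of simulated trials at 95% (91/86/56% at 90%). Where it is bounded, the upper limit is a median 14 to 19 times the lower at 95% (8 to 12 times at 90%). At 50% SD it is bounded in only 10% to 21% of trials at 95% (21% to 37% at 90%). Such intervals still tell the designers of later studies how little these data pin down ED50.

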### *Dose-relationship*

Linear:  $\text{Response} \sim E_0 + \text{Slope} * \text{Dose}$

$E_{\text{max}}$ :  $\text{Response} \sim E_0 + E_{\text{max,dose}} * \text{Dose} / (\text{Dose} + ED_{50})$

Sigmoidal:  $\text{Response} \sim E_0 + E_{\text{max,dose}} * \text{Dose}^\gamma / (\text{Dose}^\gamma + ED_{50}^\gamma)$

### *Exposure-relationship*

Linear: Response  $\sim E_0 + \text{Slope} * \text{AUC}$

$E_{\text{max}}$ : Response  $\sim E_0 + E_{\text{max,exp}} * \text{AUC} / (\text{AUC} + \text{EC}_{50})$

Sigmoidal: Response  $\sim E_0 + E_{\text{max,exp}} * \text{AUC}^\gamma / (\text{AUC}^\gamma + \text{EC}_{50}^\gamma)$

Model evaluation will include residual variability error term but will not include any random effects or covariate evaluation on fixed effect.

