## **3. Study Overview**

### **3.1. Study Design**

This is a randomized, double-blind, placebo-controlled, single-dose, parallel arm, pilot study. Healthy subjects will be randomized to one of three dose groups (low, intermediate, and high) for each drug (IFN  $\beta$ -1a and pegIFN  $\beta$ -1a) or placebo (See Table 1). The study will be conducted at one center in the United States (Spaulding Clinical Research unit in West Bend, Wisconsin).

Subjects randomized to Treatment Groups A, B, and C will stay in-house for the duration of the study and will be discharged on Day 7. Subjects randomized to Treatment Groups D, E, F, and G will stay-in house until Day 10 and return for the Day 14 assessment. Each treatment group should include equal representation of male and female subjects.

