### **Pharmacodynamic Sample Collection**

Blood samples for primary pharmacodynamic biomarker (neopterin, 5 mL) and secondary pharmacodynamic biomarker (MxA, 1 mL) assessments will be collected at the following time points:

- Screening (Day -21 to -2)
- Day 1: 0 (pre-dose), 1, 3, 6, 8, 16 h
- Day 2: 24, 32, 40 h
- Day 3, 4, 5, 6, 7
- Day 8, 9, 10, and 14 (Arms D, E, F, and G, only)

Blood samples will be collected by direct venipuncture or by inserting an IV catheter into the subject's forearm region. Each blood sample will be labeled with subject number, study number, study day, time point, event, and a barcode that matches that belonging to the subject.

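### SAP 7.5 excludes all covariates from the dose- and exposure-response models without a reason; one baseline neopterin term on E0 could sharpen Emax, ED50 and EC50 at almost no cost

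*SAP*

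**What the plan says.** SAP 7.5 fits linear, Emax or sigmoidal models separately for each drug, with placebo pooled in. The responses are the baseline-adjusted neopterin AUEC and the maximum increase from baseline, in line with SAP 7.3.1: "The primary analysis with neopterin will use baseline-adjusted AUEC and maximum increase from baseline". The models carry a residual error term, and their evaluation "will not include any random effects or covariate evaluation on fixed effect". No reason is given.

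The baseline is a single draw. Under SAP 6.1, "samples from Day 1, time 0 will be used for calculating this derived metric", and Attachment A schedules it in all arms ("Day 1: 0 (pre-dose), 1, 3, 6, 8, 16 h"). There is a fallback: "In cases where the Day 1, time 0 sample is missing or invalid, the sample collected at check-in (Day -1) will be used", and after that the screening sample. SAP 5 removes subjects with no valid baseline from baseline-adjusted metrics, so every subject in these models has some baseline value.

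The model parameters are a secondary endpoint (SAP 4.2). Among the grounds for choosing between model structures, SAP 7.5 lists "parameter uncertainty (i.e., parameter confidence intervals including zero".

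**The concern.** Subtracting a baseline differs from adjusting for it. Subtraction fixes the coefficient at 1. The error in the single pre-dose draw then enters AUEC multiplied by the length of the window, and enters the maximum increase in full. This error makes the response correlate negatively with the measured baseline. A baseline term on E0 estimates the coefficient from the data and can take that part out of the residual.

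At stake is the precision of Emax, ED50 and EC50, which are meant to help choose sensitive doses for later similarity studies. Because parameter uncertainty also bears on which structure is kept, avoidable residual variance could influence model choice as well as interval width.

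**Working it through.** **Inputs from the documents.** There are 12 subjects per arm and seven arms: 12 x 7 = 84, and 84 + 14 replacements = 98. Both stated sizes reproduce. SAP 3.2 says there was no formal sample size or power calculation, so there is no power or precision figure to reproduce. Each drug model pools three doses and placebo: 3 x 12 + 12 = 48 subjects before exclusions. The Emax structure has three parameters.

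**Assumed, because neither document gives them.** The within-arm correlation r between baseline and the modelled response (0 to 0.5), the ratio of Emax to residual SD, and ED50.

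**Step 1: effect on the standard error.** With 48 - 3 = 45 residual degrees of freedom and one added covariate unrelated to dose,

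SE ratio (with / without) = sqrt(1 - r²) x sqrt(44/43).

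| r | sqrt(1 - r²) | SE ratio | Change | Equivalent n = 48 / ratio² |
|---|---|---|---|---|
| 0 | 1.000 | 1.012 | about +1% | 46.9 |
| 0.2 | 0.980 | 0.991 | about -1% | 48.9 |
| 0.3 | 0.954 | 0.965 | -3.5% | 51.5 |
| 0.5 | 0.866 | 0.876 | about -12% | 62.5 |

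Break-even is where 1 - r² = 43/44, so r = sqrt(1/44) = 0.15. The information matrix of the Emax model at both drugs' doses gives the same ratios for Emax and ED50 (1.01, 0.965 and 0.875 at r = 0, 0.3 and 0.5). For EC50 the formula carries over only if baseline is unrelated to AUC, which randomisation does not guarantee.

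**Step 2: what subtraction leaves to gain.** Let c be the correlation between baseline and post-dose level, with equal variances (assumed). Then r² = (1 - c)/2, and before the degree-of-freedom cost the SE ratio is sqrt((1 + c)/2). At c = 0.5, 0.8 and 0.9 this gives |r| = 0.50, 0.32 and 0.22, and ratios 0.87, 0.95 and 0.975.

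**Step 3: how large r could be from noise in the draw.** Suppose noise is the only source of residual variance, and post-dose noise averages over about 10 effective samples. Then |r| = sqrt((1 - ICC)/1.1), which is 0.52 at an intraclass correlation of 0.7 and 0.30 at 0.9. That assumes every subject at a dose responds identically. If between-subject response variance equals the baseline variance, |r| = (1 - ICC)/sqrt(1 + 1.1(1 - ICC)):

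- ICC 0.7: 0.3/sqrt(1.33) = 0.26, so the SE falls by about 2%.
- ICC 0.9: 0.1/sqrt(1.11) = 0.09, so the SE rises by about 1%.

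**Step 4: effect on the confidence-interval criterion.** These are simulations of the Plegridy doses plus placebo, 12 per arm, 600 replicates per run. They count how often the 95% Wald intervals for Emax and ED50 both exclude zero. Ranges are across runs at r = 0.5.

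| ED50 (µg), residual SD as % of Emax | Without baseline | With baseline |
|---|---|---|
| 62.5, 15% | 71-75% | 88-92% |
| 31.25, 20% | 60-62% | 85-87% |
| 125, 10% | 49-54% | 68-72% |

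In the same three settings the change is +4 to +10 points at r = 0.3, -1 to +2 at r = 0.15, and -4 to 0 at r = 0. These settings are favourable. The relative SE of ED50 is 44% to 50%, just under the 1/1.96 = 51% at which a Wald interval touches zero. With Emax at 2 to 4 residual SDs, the relative SE of ED50 is 58% to 250%. There, four dose levels and 12 per arm limit precision far more than a missing covariate does.

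**The case against.** The strongest reply is that a three- or four-parameter fit to about 48 subjects without covariates is a reasonable, parsimonious choice in a pilot with no precision target. The pre-dose value is already used, by subtraction. No document supplies the correlation on which any gain depends. If subjects with higher baselines also respond more in absolute terms, that positive correlation would offset the negative one from noise. All of this stands. It limits how much can be claimed but does not explain a blanket exclusion, because the cost of the baseline term at r = 0 is only about 1% in the SE.

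A second reply also stands: the confidence-interval criterion is one of several. SAP 7.5 combines it with goodness-of-fit plots and AIC after a graphical look. It sets no confidence level and does not require both intervals to exclude zero. A reader might infer that a correct Emax model would be set aside for want of a covariate, but the SAP contains no rule that would do this by itself.

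A reader might also want sex in the model, since "Each treatment group should include equal representation of male and female subjects". That sentence states a representation target. Protocol 5.8.3.1 mentions stratification without naming a factor, and neither document reports a sex effect on neopterin. In the exposure model a sex term could do harm: if sex shifted log-AUC by 0.6 (assumed) without affecting the response, the SE would rise by about 4% for EC50 and 6% for Emax,exp.

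One further limit concerns Avonex. SAP 4.1 runs AUEC to the last on-study time point, and Attachment A samples placebo to Day 14 but Avonex to Day 7. Unless a common window is used, the baseline slope could differ between placebo and active arms in that model, and the gain from a single slope may be smaller than shown.

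**Conclusion.** The point holds as a conditional efficiency improvement. SAP 7.5 gives up, without a reason, a covariate that is already collected and that every modelled subject has. The parameters may therefore be less precise than they could be. Over assumed r from 0 to 0.5 the SEs of Emax and ED50 change by between about +1% and -12%. The same range applies to EC50 if baseline is unrelated to AUC.

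It would be too strong to say that precision is certainly lost, because below r of about 0.15 adjustment does not help. It would also be too strong to call the planned analysis biased or contradictory. A pre-dose Day 1 value for every subject is planned but not guaranteed, which is why SAP 6.1 has fallbacks. The endpoint is secondary and the study is a pilot, so this is a modest improvement to make.

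**What to change.** In SAP 7.5, replace the covariate exclusion with wording such as: 'The centred baseline neopterin value, as defined by the SAP 6.1 order (Day 1 time 0, then check-in, then screening), will enter as one prespecified additive covariate on E0 in each dose- and exposure-response model; fits without it will be reported as a sensitivity analysis.' Do not add a sex term.

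Tying the covariate to the SAP 6.1 order means that no subject has a response but an undefined covariate. Because the term acts on E0 only, Emax, ED50 and EC50 keep their meaning. The cost is a change of SAP wording, one degree of freedom of about 48 per model, and an SE about 1% larger if baseline turns out to be unrelated to response. No new data are needed.
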